1.1 Study Rationale

To advance the science in HIV-associated cervical cancer in the HAART era, this prospective feasibility trial in HIV-infected women with LACC will be performed at African AMC sites to determine and establish baseline data important for future evaluation of treatment regimens in this patient population using the standard, simple to administer, outpatient regimen of cisplatin concomitant with RT. Secondary analyses will include overall and progression-free survival. This trial represents the next step in the science of HIV-associated cervical cancer treatment for numerous reasons:

- 1) For this protocol, all participants will be receiving ART. All participants must be on combination antiretroviral therapy with an acceptable regimen that adheres to national guidelines for treatment of HIV infection. This trial would provide additional toxicity data in subjects with LACC on ART.
- 2) Most current trials in LACC in HIV-uninfected women include additional cytotoxic chemotherapy for higher risk patients (e.g. ANZOG/GOG/RTOG/NCIC/GEICO/NSGO ‘Outback’ trial), targeted therapies (e.g. bevacizumab), or additional maintenance therapy. This trial would represent the baseline of comparison for future trials in HIV-associated LACC using cisplatin in combination with other therapies.
- 3) While this study will not stratify by stage or nodal involvement, all participating sites will be required to perform baseline imaging (CT A/P with contrast) to assess tumor size and enlarged nodes. GOG trials in HIV-uninfected women with positive nodes who are treated with concomitant chemoradiotherapy with cisplatin alone have poorer survival and increased toxicity compared with those with unenlarged nodes (22-26). In this trial, we will assess whether the presence of positive nodes by imaging is a poor prognostic characteristic among HIV-infected women with LACC.

1.2 Rationale for Exploratory/Translational Testing

1.2.1 HPV DNA Testing

High-risk HPV types have been implicated in the etiology of cervical cancer (28-30), and its precursor, high-grade cervical intraepithelial neoplasia (CIN) (29,31); and anal cancer (32-33) and its putative precursor, high-grade anal intraepithelial neoplasia (AIN) (34-37). More than 100 HPV types have been identified, which by definition differ from one another by at least 10% of their DNA sequences (38). Of the HPV types conferring the highest risk for high-grade disease and invasive cancer, HPV types 16 and 18 are the most common (32,38), with HPV 16 infection being the single most common HPV type in anogenital cancer (39).

However, it is not known if the distribution of HPV types in cervical cancer developing in HIV-infected is different from that developing in HIV-uninfected women, where it has clearly been shown that HPV 16 and 18 are present in approximately 50% and 20% of cancers, respectively. We will also collect cervical and anal swabs at baseline prior to initiation of therapy, and at completion or premature discontinuation of therapy. The post-treatment samples will allow us to examine in an exploratory analysis, the effect of treatment on HPV persistence, and determine whether HPV persistence is related to disease recurrence. We also propose to study anal samples for HPV DNA at these time points. Studies have shown a relationship between cervical and anal cancer, and little is known about anal HPV in women with cervical cancer. We can also examine the effect of cervical cancer treatment on anal HPV persistence.

Therapy for cervix cancer has changed over the last decade. Chemotherapy has been shown to be beneficial and has been added to our armamentarium of surgery and radiation. Nevertheless, in an era of personalized medicine, the potential biological differences of cervix cancer associated with different HPV types and host variation have not been adequately evaluated as determinants of cervix cancer outcome and/or response to therapy. Prior studies were conducted in the era of radiation alone, not concomitant chemoradiotherapy, and none address HIV-associated cervical cancer (40-42). Moreover, cervix cancer in an advanced state and in the setting of HIV has a poor prognosis. Since HPV types associated with cancer have divergent risks and associations with tumor types, we expect that knowledge of the HPV type will help to identify patients most at risk for treatment failure, recurrence, and response to surgery, radiation and/or chemotherapy.

Although detection of an oncogenic HPV type is associated with increased risk of anogenital cancer, recent studies of cervical lesions suggest that differences in the genome sequence within variants of a given HPV type, such as HPV 16, may substantially affect the level of risk. Thus, “European” or “prototype” variants of HPV 16 were associated with lower risk of CIN 2 or 3 and cervical cancer than were “non-European” or “non-prototype” variants (43). This was shown to be the case for AIN as well compared to “prototype” HPV 16 variants. MSM with anal “non-prototype” HPV 16 variants were more than three times as likely to develop AIN 3 (43-44). In a study by Palefsky et al., an elevated risk for AIN 2 or 3 was

associated with infection with G131 European variants of the HPV 16 E6 protein when compared with the prototype HPV 16 strain (44).

Amino acid differences in the E6 and E7 proteins are likely to be at least partly responsible for the differential pathogenicity of the various HPV types. However, the amino acid sequences of these proteins vary not only across HPV types, but within type as well. More than 25 sequence variants of HPV 16 have been reported, and a phylogeny-based classification incorporating the L1, L2, and E6 genes has been proposed by Yamada et al (45). Differential pathogenicity of HPV 16 variants has been reported for cervical HSIL (43,46-47), invasive cervical cancer (48), and anal HSIL (49). In a study of variants in the L1 region, Hildesheim et al (50) reported that detection of non-European variants, as is typically found in Africa, was associated with increased risk of cervical cancer. Nothing is currently known of the HPV variants in HIV-associated cervical cancer, nor is there an understanding of concomitant anal HPV infection in the setting of cervical cancer and HIV in Africa or the US.

1.2.2 DNA Methylation in HIV-associated cervical cancer

DNA methylation is a mechanism used by cells to regulate gene expression (51-53). It involves the addition of a methyl group to cytosine nucleotides by enzymes called DNA methyltransferases (54). Typically, the methylated cytosines are clustered in chromosomal regions rich in cytosine and guanine dinucleotides (CpG islands) found in the promoter region, which is involved in regulating gene expression. In general, methylation of this region results in altered expression of the adjacent gene. The mechanism for this is not entirely clear but involves the disruption of the association of transcription factors with the DNA. DNA methylation is also associated with histone deacetylation, which compacts the chromatin and further represses gene expression.

DNA methylation has an important role in tumorigenesis (55). Methylation-induced alteration of genes that limit cell growth, termed tumor suppressor genes, is an important step in tumorigenesis, in addition to point mutations or deletions. Many tumor suppressor genes are specifically methylated in tumors but not in normal tissues. Methylation of tumor suppressor genes has been detected in virtually every type of malignancy, including cervical cancer. The profile of methylated genes appears relatively specific for each tumor type. For example, p16INK4a gene methylation is noted in many different tumors, such as colorectal, lung, breast, and cervical carcinoma. But other genes such as p15INK4b are methylated in leukemia and lymphoma, but not in lung, colon, or breast cancers (56). In other words, many tumors have gene methylation profiles that are specific for the tumor type.

In prior studies of CIMP profiles in women with different grades of CIN and cancer, there are differences in the quantity and profile of methylated genes across grades of CIN and cervical cancer (57-61). Differential methylation of MGMT, for instance, exists across all grades of CIN and cancer appears to be a late event.

There is also differential methylation with other genes, such as CDKN2A gene, which expresses the p16ink4A protein. In addition to the gene that encodes for p16ink4A and MGMT, others include HIC1, APC, RAR β , GSTP1, Fas, MMP-1, and TNF- α . Little is known about methylation in cervical cancer tumors of HIV-infected women.

The predictive nature and timing of gene methylation in identifying cervical cancer recurrences have not yet been elucidated. We plan to examine the methylation profile in cervical and anal swab samples from participants in this trial and will, in a preliminary fashion, examine their relationship to disease recurrence in our cohort.

1.2.3 HPV Serology

Antibodies to conformational epitopes on synthetically produced virus-like particles (VLPs), structurally similar to the HPV virion, have been shown to develop in response to HPV infection (62-65). Serologic responses directed at type-specific epitopes on VLPs are often detectable when there is clinical evidence of disease. Serologic titers can be quantified and related to clinical disease status (63, 65-66). In fact, it appears that higher titers might correlate with worsening grade CIN and cancer (67). Neither seropositivity nor antibody titers have been explored as a marker for persistence or recurrence in HIV-associated cervical cancer.

2.0 STUDY OBJECTIVES

2.1 Hypotheses

- 2.1.1 Treatment compliance will be comparable to what has been previously reported in retrospective studies (27).
- 2.1.2 The toxicity of weekly cisplatin in HIV-infected women on HAART is worse than that reported in HIV-uninfected women but manageable with limited dose reductions and dose delays.
 - 2.1.2.1 Recurrence patterns for HIV-associated LACC will be similar to that in HIV-uninfected women with LACC.
 - 2.1.2.2 Patients with poorly-controlled HIV (defined as CD4 count of $\leq 200/\mu\text{L}$ and/or HIV viral load ≥ 400 copies/mL) will have higher likelihood of distant recurrences.
- 2.1.3 The PFS at 1 year in HIV-infected women on ART who complete the prescribed cisplatin and RT doses of concomitant chemoradiotherapy with weekly cisplatin is similar, stage for stage, to the PFS in HIV-uninfected women stage for stage in LACC.
- 2.1.4 The subset of participants with poorly-controlled HIV as defined by baseline CD4 T-cell count and viral load will have worse PFS when compared with participants with well-controlled HIV infection.
- 2.1.5 Baseline measures of HPV types and strain variants, gene methylation patterns, and HPV serology and/or changes induced by therapy will be associated with the risk of subsequent recurrence of HIV-associated LACC.

2.2 Primary Objectives

- 2.2.1 To determine if it is feasible to administer a regimen of cisplatin/RT in HIV-infected women with LACC on ART. This regimen is considered standard therapy for women with LACC who are not HIV infected. Feasibility will be assessed based on:
 - 2.2.1.1 Treatment completion proportion – the proportion of participants who complete the cisplatin/RT regimen
 - 2.2.1.2 Screening ratio: the number of potential participants screened per enrolled participant
 - 2.2.1.3 Availability proportion: follow-up completion proportion at 6 and 12 months

2.2.2 To evaluate the safety and tolerability of concomitant chemoradiotherapy with cisplatin in HIV-infected women with LACC who are also receiving concomitant ART.

2.3 Exploratory Objectives

2.3.1 To determine the 1-year progression-free survival (PFS) of HIV-infected women with locally-advanced invasive cervical cancer (LACC) Stage IB, II, III, and IVA who receive weekly cisplatin concomitant with radiotherapy and ART.

2.3.1.1 Determine PFS in all registered participants, regardless of completion (intent to treat-ITT)

2.3.1.2 Determine the PFS in the subset of participants who complete the prescribed chemotherapy/ radiotherapy

2.3.1.3 Compare PFS in these subjects with PFS of HIV-uninfected subjects as reported in the literature, stage for stage.

2.3.2 To describe the effects of treatment on participants' CD4 counts, HIV viral load and concurrent AIDS-defining conditions.

2.3.3 To describe cervical cancer recurrence patterns in HIV-infected participants with LACC defined as loco-regional and/or distant recurrences.

2.3.4 Determine 1-year overall survival and causes of death (i.e., cancer-related, HIV-related, or other).

2.3.5 To evaluate the effects of weekly cisplatin concomitant with radiotherapy on adherence to ART.

2.3.6 Collect serum and cervical and anal swab material for the following exploratory analyses:

2.3.6.1 To describe the distribution of HPV DNA types and HPV strain variants in cervical and anal swabs collected at baseline, prior to initiation of study treatment;

2.3.6.2 To assess the concordance between HPV DNA types and HPV strain variants detected in cervical and anal swabs collected at baseline, prior to initiation of study treatment;

2.3.6.3 To investigate the effect of study treatment on HPV persistence in cervical and anal swabs and its relationship to cervical cancer persistence or recurrence;

2.3.6.4 To describe the gene methylation profiles in cervical and anal swabs collected at baseline, prior to initiation of study treatment;

- 2.3.6.5 To investigate the relationship between baseline gene methylation profiles and cervical cancer persistence or recurrence;
- 2.3.6.6 To measure serum antibody titers to HPV 16 and HPV 18 at baseline and on study, and to determine whether baseline titers or changes during therapy correlate with cervical cancer persistence or recurrence.

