4.2 Cancer Treatment Therapies

4.2.1 Radiation Therapy

See dose table below [\(Section 4.6\)](#) for details and appropriate fractionation schemes.

- 41.4-45.0 Gy/1.8 Gy per fraction/23-25 fractions/five weeks pelvic RT.
- 35-43.6 Gy intracavitary brachytherapy in one to two implants LDR or 18-28 Gy intracavitary brachytherapy in 2-4 fractions HDR.
- 5.40 - 9.00 Gy/1.8 Gy/3-5 fractions/3-5 days parametrial boost to involved parametria.
- Overall treatment time not to exceed eight weeks.

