4.7 Duration of Study

Each participant should complete the study treatment unless disease progression occurs or toxicity prohibits further therapy. Regardless of whether the treatment is completed, the participant should be followed at least at month 6 and month 12 after the completion of treatment.

Participants should be contacted by clinic staff by appropriate communication mechanisms in order to encourage and maintain the participant's follow-up with their study visits. Follow-up mechanisms may be done by phone, text, email or reminder cards. If a participant is unable or unwilling to come to the clinic for a follow-up visit, clinic staff may obtain information regarding the patient's general health, adverse events, medication changes, or other appropriate changes verbally or via an email or text message from the participant. This information must also be documented within the participant's medical record by a note or copy of the email, phone call, or text message.

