9.2 Exploratory Outcome Measures

- 9.2.1 Progression Free Survival is defined as the date from protocol registration to date of first documented reappearance (recurrence) or progression of disease or death. Since all subjects will be followed for 12 months after treatment, we will determine the 1-year PFS rate.
- 9.2.2 Recurrence is defined as increasing clinical, radiological or histological evidence of disease since study entry.
 - 9.2.2.1 Site of First Recurrence (e.g., para-aortic or supraclavicular lymph nodes, lung, liver, bone, etc.) will also be documented.
- 9.2.3 Overall Survival will be defined as observed length of life from entry to protocol to death; or for living participants, the date of last contact.
- 9.2.4 Local Control is coded as successful if no recurrence or disease progression is within the pelvic field. Persistence of tumor three months after completion of therapy will be coded as a failure. It is coded as a failure if there is any clinically documented evidence of recurrence or disease progression within the pelvic field.
- 9.2.5 Effects of treatment on the participant's HIV disease status will be determined by tracking the CD4 count, viral load, and concurrent AIDS-defining conditions.
- 9.2.6 Effects of treatment on the participant's HPV status, and the association of these factors with treatment outcomes, will be determined by measuring HPV DNA types and strain variants and gene methylation in cervical and anal swabs, and by measuring antibodies to HPV in serum.

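### PFS in treatment completers is counted from registration, although completer status is reached only 5 to 9 weeks later, so the estimate is biased upward unless there are no early events

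*Combined protocol and SAP*

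**What the plan says.** Section 9.2.1 gives one definition of PFS for everyone: "Progression Free Survival is defined as the date from protocol registration to date of first documented reappearance (recurrence) or progression of disease or death". Objective 2.3.1.2 applies it to completers: "Determine the PFS in the subset of participants who complete the prescribed" chemotherapy and radiotherapy. Objective 2.3.1.1 plans an ITT estimate in all registered women beside it, and 2.3.1.3 plans a stage-for-stage comparison with published PFS in HIV-uninfected women. Hypothesis 2.1.3, which predicts similarity to HIV-uninfected women, is worded for the completers: "The PFS at 1 year in HIV-infected women on ART who complete the prescribed cisplatin and RT doses".

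Completion comes well after registration. Section 4.2.1 limits treatment as follows: "Overall treatment time not to exceed eight weeks". Section 4.6.8 places the end of radiotherapy between day 50 and day 56, and 4.6 allows up to 7 days between enrollment and the start of radiotherapy. Section 4.7 links completion to outcome: "Each participant should complete the study treatment unless disease progression occurs or toxicity prohibits further therapy". Section 11.1 defines completion by cisplatin alone, and under 4.2.2 the sixth weekly dose falls on day 36.

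For PFS, 11.1 plans Kaplan-Meier curves. It mentions no landmark, delayed entry or time-dependent completion status.

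**The concern.** Completer status is decided after the clock has started. A woman who dies during treatment cannot be in the subset, and one with clinically evident progression is unlikely to be. Those who are in it bring several weeks in which, for the most part, no event could have been counted. This is guaranteed-time bias. It raises the completer estimate even if completing treatment has no effect and completers are no fitter than other women.

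The bias favours the trial's own hypothesis, because 2.1.3 predicts that completers do about as well as HIV-uninfected women. The result may also be reused: section 1.1 presents the trial as a baseline for later trials in this population, and section 1.0 says that its estimates will inform a phase II trial.

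**Working it through.** The documents state no PFS rate, event count or precision target for PFS, so there is no planned figure to reproduce. The check asks how large the inflation could be.

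**Inputs from the documents**
- Clock start: registration (9.2.1).
- Guaranteed time G: 5 weeks if completion means cisplatin only (day 1 to day 36, 4.2.2 and 11.1); 8 weeks for full cisplatin and radiotherapy (4.2.1, 4.6.8); 9 weeks if the 7-day gap in 4.6 is added.
- Expected completers: the 70% completion target in 11.2 applied to 38 or 45 women gives 26.6 or 31.5, so 27 to 32.

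**Assumption**
- True 1-year PFS, S, between 0.50 and 0.70.

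**Step 1: constant hazard.** With no prognostic difference between completers and others, completer PFS at 52 weeks from registration is S(52)/S(G) = S^((52-G)/52). For S = 0.50 and G = 8 this is 0.50^(44/52) = 0.556.

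| True 1-year PFS | G = 5 weeks | G = 8 weeks | G = 9 weeks |
|---|---|---|---|
| 0.50 | 0.534 (+3.4 points) | 0.556 (+5.6) | 0.564 (+6.4) |
| 0.60 | 0.630 (+3.0) | 0.649 (+4.9) | 0.655 (+5.5) |
| 0.70 | 0.724 (+2.4) | 0.739 (+3.9) | 0.745 (+4.5) |

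A simulation of 2,000,000 exponential event times, with completion random among women event-free at G, gave the same values to within 0.001. Counting 52 weeks from completion instead returned 0.50, 0.60 and 0.70 at G = 8. That exact return depends on the constant hazard.

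**Step 2: what a constant hazard implies.** The share of first-year events falling before week 8 is (1 - S^(8/52))/(1 - S). For S = 0.50 this is 0.101/0.50, about 20%; for S = 0.60, 0.076/0.40, about 19%; for S = 0.70, 0.053/0.30, about 18%.

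**Step 3: fewer early events.** If a share f of first-year events falls before completion, completer PFS is S/(1 - f(1 - S)).

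| f | S = 0.50 | S = 0.60 | S = 0.70 |
|---|---|---|---|
| 0 | 0 | 0 | 0 |
| 2% | +0.5 points | +0.5 | +0.4 |
| 5% | +1.3 | +1.2 | +1.1 |
| 10% | +2.6 | +2.5 | +2.2 |

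**Step 4: scale.** The approximate 95% half-width is 1.96 x sqrt(S(1 - S)/n). With n = 27 it is 18.5 points at S = 0.60 and 17.3 at S = 0.70; with n = 32 it is 17.0 and 15.9.

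**The case against.** The strongest objection concerns size. A constant hazard needs 18-20% of first-year events to occur during treatment, and the schedule gives little chance to record that many. CT is done at baseline and at months 6 and 12 after treatment (5.1.1, 5.3.2, 5.3.4). The one physical examination scheduled within the treatment weeks is on day 22 (5.2.1), with the next at completion (5.2.2). Entry requires a life expectancy above 12 months and ECOG status of 2 or less (3.1). This stands: 4-6 points is an illustration, not a forecast.

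A reader might infer that no woman who progresses during treatment can be a completer, so that the window is event-free by construction. That holds for deaths. For progression the documents do not go so far. Section 4.7 names progression as a reason for not completing, but 8.1 does not list it among the reasons for permanent discontinuation; these sections need to be reconciled. Undetected progression would not stop treatment in any case.

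A reader might also infer that the trial will wrongly conclude that completers match HIV-uninfected women. No test, margin or sample size is attached to 2.1.3, the PFS objectives are exploratory, and the ITT estimate, which does not have this bias, is planned. The shift is also small beside the sampling error. These points lower the priority. They do not remove the defect, since the bias runs one way, is not reflected in the confidence interval, and sits in the estimate that 2.1.3 names.

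Finally, a landmark does not remove the selection of fitter women into the completer group. That is true, and is why ITT PFS should lead the literature comparison.

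**Conclusion.** The concern holds as to direction: registration-based PFS in completers is biased upward, or unbiased only if there are no deaths or progressions before completion. The size cannot be fixed from the documents. For a true 1-year PFS of 50-70%, it is zero with no early events, about 0.5 to 2.6 points if 2-10% of first-year events fall before completion, and about 4-6 points under a constant hazard with 8 weeks of guaranteed time. The cisplatin-only reading of completion in 11.1 lowers the constant-hazard figure to 2.4-3.4 points. All of this sits inside a 95% half-width of about 16-18 points. It is a modest flaw in an exploratory analysis, worth correcting because the correction is cheap.

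**What to change.** Change 2.3.1.2 and 11.1 as follows.

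- Define completion once for this analysis, as completion of cisplatin and radiotherapy.
- Estimate completer PFS from one fixed landmark, for example day 56 from the start of treatment, among women alive and progression-free on that day. Classify completion as it stands on that day, and show non-completers from the same landmark. Each woman's own end of treatment would not serve, because it gives non-completers no common starting point.
- Label the result as conditional on completing treatment.
- Leave the registration-based definition in 9.2.1 unchanged for ITT PFS. Report ITT PFS beside the landmark result as the main estimate for 2.3.1.3 and hypothesis 2.1.3, and do not use registration-based completer PFS for that comparison.

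Only analysis wording changes, and no visit is added. The costs are these:

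- The completer estimate will be less favourable.
- A few women are excluded at the landmark, and anyone finishing after day 56 counts as a non-completer; report both numbers.
- For women who stop early, the visit in 5.2.2 falls soon after stopping, so their day-56 status may rest on later contact.
- A full year from the landmark falls close to the month-12 visit (+/- 4 weeks), so some women may be censored just before it.
- Selection of fitter women remains.
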